3.4 Protocol deviations

Important protocol deviations are defined as those deviations from the protocol likely to have a meaningful impact on the primary efficacy outcomes for an individual subject. Important protocol deviations will be identified and classified by the deviation types defined in the appropriate protocol-specific document. All protocol deviations will be reviewed as part of the ongoing data cleaning process and all important deviations will be identified and documented prior to unblinding to confirm exclusion from Per Protocol Set (PPS), Pharmacokinetics Per-Protocol Set (PK-PPS) and Pharmacodynamics Per-Protocol Set (PD-PPS). The exclusion from PPS is limited to the Double-Blind Period, ie. only subjects with important protocol deviations prior to re-randomization at Visit 7 (Week 12) will be excluded from PPS. Subjects with important protocol deviations after Visit 7 (Week 12) will not be excluded from PPS.

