3.6.3 Safety Set (SS)

The SS consists of all randomized subjects who received at least 1 dose of the IMP.

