3.6.6 Pharmacokinetics Per-Protocol Set (PK-PPS)

The PK-PPS is a subset of the FAS, consisting of those subjects who had no important protocol deviations affecting the pharmacokinetic variables, as confirmed during ongoing data cleaning meetings prior to database lock.

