5.2 Protocol deviations

Important protocol deviations will be identified and classified by the deviation types. Following different important protocol deviation types will be classified: inclusion criteria deviation, exclusion criteria deviation, withdrawal criteria deviation, prohibited concomitant medication use, incorrect treatment or dose, treatment non-compliance, and procedural non-compliance.

Summary tables of the number and percentage of subjects with an important protocol deviation will be provided including a summary of subjects excluded from the PPS, PK-PPS, and PD-PPS due to important protocol deviations. Summary tables will be presented for FAS and Baseline treatment groups.

A listing of all important protocol deviations identified at the data evaluation meeting will be presented by subject for all subjects in the RS, and will include deviation type and description.

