The number and percentage of subjects with AbAb levels above the specified cut point will be summarized.

In addition, the time point of the first occurrence of AbAb positivity during the Double-Blind Period, and the entire treatment period (excluding Baseline and pre-treatment) will be summarized for each treatment group.

All individual subject-level AbAb results will be listed including the screening assay, confirmatory assay, and titres if applicable. Note, that titre results will only be available, if the confirmatory assay is positive.

Immunogenicity data will be summarized and listed using the PK-PPS analysis set.

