10 SAFETY ANALYSES

All safety summaries and listings will be performed using all subjects in the SS.

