The incidence of TEAEs will be summarized by MedDRA SOC, high level term, and PT. Tables with incidences of classified TEAEs by maximum intensity, by relationship, and by subject number will be provided. The incidence of non TEAEs, non-serious TEAEs above the reporting threshold of 5% of subjects and relationship will be summarized. Furthermore the incidence of all TEAEs, serious TEAEs, non-serious TEAEs, and TEAEs leading to study discontinuation and/or permanent withdrawal of study medication, adverse drug reactions, fungal infectious disorder TEAEs, opportunistic infection (including tuberculosis) TEAEs, malignant or unspecified tumor TEAEs, malignant tumor TEAEs, major cardiovascular event TEAEs, haematopoietic cytopenias TEAEs, neuropsychiatric events TEAEs, inflammatory bowel disease TEAEs, hypersensitivity and anaphylactic Reaction TEAEs, hepatic events TEAEs, and TEAEs by timing of onset relative to AbAb Status will be summarized. In addition, an overall summary table will be provided.

The tables will be split into the Double-Blind Period and the complete treatment period (exception non TEAE table and TEAEs by timing of onset relative to AbAb Status).

Presentations for the Double-Blind Period will summarize AEs that start prior to or at Visit 7 (see details given above) by treatment group as randomized for the Double-Blind Period.

Presentations for the complete treatment period will only summarize AEs that occur under treatment with bimekizumab, irrespective of the treatment period. For summaries of the bimekizumab 160mg, 160mg with loading dose and bimekizumab 320mg treatment groups, patients randomized to Placebo or bimekizumab 16mg at Baseline will only be included with AEs that start in the Dose-Blind Period. The all bimekizumab treatment group will also present AEs occurring under bimekizumab 16mg treatment in the Double-Blind Period. AEs for each subject will be summarized based on the treatment actually received at the onset of each particular AE.

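### Antibody results are reported only on the PK per-protocol set, so treated antibody-positive subjects can be missing from the incidence and titre listing, and counts may not match the safety and efficacy tables

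*SAP*

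**What the plan says.** Immunogenicity is a secondary objective in its own right (Protocol 3.2, SAP 2.1.2). For its reporting, SAP 9.2 says: "Immunogenicity data will be summarized and listed using the PK-PPS analysis set". The paragraph before it says: "All individual subject-level AbAb results will be listed including the screening assay, confirmatory assay, and titres if applicable".

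SAP 3.6.6 defines the set: "The PK-PPS is a subset of the FAS, consisting of those subjects who had no important protocol deviations affecting the pharmacokinetic variables". SAP 5.2 lists the types of important deviation, among them "incorrect treatment or dose, treatment non-compliance, and procedural non-compliance".

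Two other uses of antibody status rest on wider sets:
- SAP 10.2 plans that "TEAEs by timing of onset relative to AbAb Status will be summarized". SAP 10 fixes the population for such tables: "All safety summaries and listings will be performed using all subjects in the SS". Under SAP 3.6.3, "The SS consists of all randomized subjects who received at least 1 dose of the IMP".
- SAP 4.8 and 8.4 use treatment-emergent AbAb status as a subgroup for the primary and secondary efficacy variables, which SAP 8.1.2 and 8.2 analyse on the FAS.

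SAP 3.1 also promises a complete set of listings covering all documented and derived data.

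**The concern.** A subject who received bimekizumab and formed antibody is informative about immunogenicity whether or not dosing was regular. Exclusion from the PK-PPS depends on events that can occur after randomization, so the antibody incidence comes from a selected group of treated subjects.

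The exclusion is also broad. The PD-PPS ties a deviation to the time point it affects (SAP 3.6.7), but the PK-PPS removes the subject entirely. SAP 3.4 limits the reach of late deviations for one set only: "Subjects with important protocol deviations after Visit 7 (Week 12) will not be excluded from PPS". No such limit is written for the PK-PPS. As the text stands, a PK-relevant deviation in the Dose-Blind Period could also remove that subject's antibody results from the first 12 weeks.

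At stake are the incidence reported for a secondary objective, the completeness of the titre listing, and a reader's ability to trace AbAb-positive subjects across the immunogenicity, safety and efficacy tables.

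**Working it through.** The plan gives no figure to reproduce. The check compares analysis sets and then bounds the effect under stated assumptions.

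**1. Sets side by side**
- AbAb summary and listing: PK-PPS (SAP 9.2, 3.6.6).
- Adverse events by onset relative to AbAb status: SS (SAP 10, 10.2).
- Efficacy by AbAb status: FAS endpoints (SAP 8.1.2, 8.2, 8.4).

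SAP 9.1 and the biomarker paragraph of 9.2 each name a second set for concentrations and biomarkers. The antibody sentence names only one. SAP 3.7 uses actual treatment for both the SS and the PK-PPS, so moving between them changes who is counted, not the treatment rule.

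**2. When the tables differ**
- Denominator: differs from the SS if any excluded subject has antibody data.
- Positive count: differs only if at least one excluded subject is AbAb-positive.
- Listing: omits results, including titres, for any excluded subject with samples.

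**3. Effect on the rate**
Let p be the PK-PPS rate, f the fraction of treated subjects excluded, and k the excluded subjects' antibody rate relative to p. The all-treated rate is (1-f)p + fkp, so

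ratio = all-treated rate / PK-PPS rate = 1 + f(k-1).

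Neither f nor k is in the documents. Assume f = 0.05 to 0.15 (10 to 30 of 200) and k = 0 to 2:
- f = 0.05: k = 0 gives 0.95; k = 1 gives 1.00; k = 2 gives 1.05.
- f = 0.15: k = 0 gives 0.85; k = 1 gives 1.00; k = 2 gives 1.15.

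A ratio below 1 means the PK-PPS overstates the all-treated rate; above 1, it understates it.

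**4. Illustration in counts (assumed)**
Take 200 treated, 20 positive (10.0%) and 10 excluded (f = 0.05):
- 0 of the excluded positive: 20/190 = 10.5%.
- 1 positive: 19/190 = 10.0%.
- 5 positive: 15/190 = 7.9%.
- All 10 positive: 10/190 = 5.3%.

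The last two are extreme. They imply k = (5/10)/(15/190) = 6.3 and k = (10/10)/(10/190) = 19, well outside the range in step 3.

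**5. One arm (assumed)**
With 40 planned per arm and 4 positive (10.0%), losing one positive subject gives 3/39 = 7.7%, and losing two gives 2/38 = 5.3%. These are falls of 2.3 and 4.7 percentage points.

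**6. Which counts are comparable**
The efficacy subgroup counts first positivity only up to Week 12 (SAP 4.8, 8.4). SAP 9.2 reports first positivity for the Double-Blind Period and for the entire treatment period. Only the Double-Blind Period count can be set against the efficacy subgroup. The full-period count would differ on any set.

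**The case against.** The strongest reply is that little may be lost and that the choice is defensible.

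- **Exclusion criteria are not shown.** Protocol 15.6 and SAP 3.4 place the detailed deviation criteria in a separate document. A reader might infer that every subject with an incorrect or missed dose leaves the PK-PPS. The SAP does not say so: the deviation must be important and must affect PK variables. Dosing is by site staff in the clinic (Protocol 7.2, 7.7). This stands.
- **The FAS step may remove nobody.** SAP 6.1 allows for the SS and FAS being identical. This stands.
- **No breach of the protocol.** Protocol 15.5.2 names no set for antibody status, and SAP 9.2 determines it at visits with concentration sampling, so the PK set is an understandable choice. That explains the choice, but does not make the set suitable for a separate secondary objective.
- **Excluded subjects are not hidden.** Their adverse events remain in the SS tables. SAP 5.1 lists analysis-set membership, and SAP 5.2 summarises PK-PPS exclusions and lists important deviations for the Randomized Set. It would therefore be wrong to infer that such a subject vanishes from the report. What can be missing is the antibody result and titre.
- **The listing sentences can be reconciled.** The first may say which results are listed, and the second for whom. That reading is possible, so this is a tension rather than a flat contradiction. It still leaves the complete-listings rule in SAP 3.1 unmet if anyone with samples is excluded.

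**Conclusion.** The concern holds in conditional form. Following SAP 9.2 as written can leave a treated, AbAb-positive subject out of the immunogenicity incidence and titre listing, while the same subject counts in the SS adverse-event table and possibly in the FAS subgroup.

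Two stronger readings are not supported. One is that the counts will fail to match: that depends on whether anyone is excluded and whether any of them is positive, which the documents cannot show. The other is that the incidence is understated: nothing in the documents says excluded subjects form antibody more often, and if they form it less often the bias reverses.

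The 0.85 to 1.15 range rests entirely on the assumed f and k, and includes no effect. The point concerns a secondary objective and leaves the primary dose-response test untouched. It is worth correcting because the remedy is cheap and removes an exclusion that can depend on post-randomization events.

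**What to change.** In SAP 9.2, replace the antibody population sentence so that:
- AbAb status is summarised for all SS subjects with at least one post-dose AbAb sample;
- all AbAb results, including confirmatory results and titres, are listed for the SS;
- the PK-PPS antibody table is kept as supportive, and concentrations stay on the sets named in SAP 9.1.

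A footnote should say that only the Double-Blind Period antibody count is comparable with the Week 12 efficacy subgroup.

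The cost is a short text change and a rerun of the antibody tables and listing, with no new samples. The downside is that subjects with irregular dosing enter the main table; the supportive PK-PPS table shows whether that matters.

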10 SAFETY ANALYSES

All safety summaries and listings will be performed using all subjects in the SS.

10.1 Extent of exposure

The duration of exposure and time at risk will be summarized for the Double-Blind Period and the entire treatment period. For the entire treatment period the duration of exposure and time at risk will be calculated for bimekizumab 160mg and 160mg with loading dose, bimekizumab 320mg, and all bimekizumab. The calculation of exposure duration and time at risk for the all bimekizumab group is different from that of the other two groups. For all bimekizumab the duration of exposure and time at risk will include the time a subject received any dose of bimekizumab (including 16mg) while for the other two treatment groups only the time a subject received 160mg, 160mg with loading dose, or 320mg will be included into the calculation.

Duration of exposure Double-Blind Period

The duration of exposure (in days) during the Double-Blind Period will be calculated as:

$$\begin{aligned} \text{Duration of exposure} &= \text{Date of last injection (double - blind period)} \\ &- \text{Date of first injection (double - blind period)} + 28 \end{aligned} \quad (16)$$

28 days refer to one half-life of bimekizumab.

Note: If the date of last injection (Double-Blind Period) + 28 extends to a date beyond the date of first injection (Dose-Blind Period), then this calculation reverts to

$$\begin{aligned} \text{Duration of exposure} &= \text{Date of first injection (dose - blind period)} \\ &- \text{Date of first injection (double - blind period)} + 1 \end{aligned} \quad (17)$$

For subjects who die during the Double-Blind Period, then this calculation reverts to:

$$\begin{aligned} \text{Duration of exposure} &= \text{Date of death} - \text{Date of first injection (double} \\ &- \text{blind Period)} + 1 \end{aligned} \quad (18)$$

Duration of exposure entire treatment period

For subjects who do not switch study treatments, who receive bimekizumab 160mg with loading dose at Baseline, or who receive bimekizumab 16mg and will be summarized under all bimekizumab group:

$$\begin{aligned} \textit{Duration of exposure} \\ = \textit{Date of last injection} - \textit{Date of first injection} + 28 \end{aligned} \quad (19)$$

Note: If the date of last injection +28 extends to a date beyond the final visit date (not including SFU), then this calculation reverts to:

$$\begin{aligned} \textit{Duration of exposure} \\ = \textit{Date of last visit (not including SFU)} \\ - \textit{Date of first injection} + 1 \end{aligned} \quad (20)$$

For subjects who die, then this calculation reverts to:

$$\textit{Duration of exposure} = \textit{Date of death} - \textit{Date of first injection} + 1 \quad (21)$$

For subjects who receive Placebo or bimekizumab 16mg in the Double-Blind Period and will be summarized under their Dose-Blind treatment in the overall table group bimekizumab 160mg or 320mg, or subjects who received Placebo and will be summarized in the overall table under their Dose-Blind treatment:

$$\begin{aligned} \textit{Duration of exposure} \\ = \textit{Date of last injection} - \textit{Date of first injection (dose} \\ - \textit{blind period)} + 28 \end{aligned} \quad (22)$$

Note: If the date of last dose +28 extends to a date beyond the final visit date (not including SFU), then this calculation reverts to:

$$\begin{aligned} \textit{Duration of exposure} \\ = \textit{Date of last visit (not including SFU)} \\ - \textit{Date of first injection (dose - blind period)} + 1 \end{aligned} \quad (23)$$

For subjects who die during the Dose-Blind Period, then this calculation reverts to:

$$\begin{aligned} \textit{Duration of exposure} \\ = \textit{Date of death} - \textit{Date of first injection (dose} \\ - \textit{blind period)} + 1 \end{aligned} \quad (24)$$

The sum over all duration of exposure (in years) will be calculated for the total subject-years of duration of exposure.

The duration of exposure will be summarized by treatment group using descriptive statistics. A by-subject listing of date of first and last dose in Double-Blind Period, the date of first and last dose in Dose-Blind Period and the duration of exposure during Double-Blind Period and under bimekizumab treatment (any dose of bimekizumab) will be performed.

Time at risk Double-Blind Period

For subjects who complete the final visit of the Double-Blind Period and continue to the Dose-Blind Period:

$$\begin{aligned} \text{Time at risk} &= \text{Date of first injection (dose – blind period)} \\ &\quad - \text{Date of first injection (double – blind period)} + 1 \end{aligned} \quad (25)$$

For subjects who discontinue on or prior to the final visit of the Double-Blind Period, use the minimum of the following:

$$\begin{aligned} &\text{Date of last injection (double – blind period)} \\ &\quad - \text{Date of first injection (double – blind period)} + 140 \end{aligned} \quad (26)$$

$$\begin{aligned} &\text{Date of final contact} - \text{Date of first injection (double – blind period)} \\ &\quad + 1 \end{aligned} \quad (27)$$

$$\begin{aligned} &\text{Date of last visit (not including SFU)} - \text{Date of first injection (double} \\ &\quad - \text{blind period)} + 1 \end{aligned} \quad (28)$$

where 140 days refers to 5*half-life of bimekizumab.

For subjects who die during the Double-Blind Period, then this calculation reverts to:

$$\text{Date of death} - \text{Date of first injection (double – blind period)} + 1 \quad (29)$$

Time at risk entire treatment period

For subjects who do not switch study treatments, who receive bimekizumab 160mg with loading dose at Baseline, or who receive bimekizumab 16mg and will be summarized under all bimekizumab group:

For subjects who complete the Dose-Blind Period and enter the extension study:

$$\text{Time at risk} = \text{Date of Visit 16 (Week 48)} - \text{Date of first injection} + 1 \quad (30)$$

For subjects who die prior to the final visit:

$$\text{Time at risk} = \text{Date of death} - \text{Date of first injection} + 1 \quad (31)$$

For all other subjects, use the minimum of the following:

$$\text{Date of last injection} - \text{Date of first injection} + 140 \quad (32)$$

$$\text{Date of final contact} - \text{Date of first injection} + 1 \quad (33)$$

For subjects who receive Placebo or bimekizumab 16mg in the Double-Blind Period and will be summarized under their Dose-Blind treatment in the overall table with bimekizumab 160mg or 320mg, or for subjects who receive Placebo and will be summarized in the overall table under their Dose-Blind treatment:

For subjects who complete the Dose-Blind Period and enter the extension study:

$$\begin{aligned} \text{Time at risk} &= \text{Date of Visit 16 (Week 48)} \\ &\quad - \text{Date of first injection (dose - blind period)} + 1 \end{aligned} \quad (34)$$

For subjects who die during the Dose-Blind Period:

$$\begin{aligned} \text{Time at risk} &= \text{Date of death} - \text{Date of first injection (dose} \\ &\quad - \text{blind period)} + 1 \end{aligned} \quad (35)$$

For all other subjects, use the minimum of the following:

$$\begin{aligned} &\text{Date of last injection} - \text{Date of first injection (dose - blind period)} \\ &\quad + 140 \end{aligned} \quad (36)$$

$$\begin{aligned} &\text{Date of final contact} - \text{Date of first injection (dose - blind period)} \\ &\quad + 1 \end{aligned} \quad (37)$$

The sum over all time at risk (in years) will be calculated for the total subject-years of time at risk.

The days on treatment and days on bimekizumab treatment will be calculated as follows:

$$\begin{aligned} \text{Days on treatment} \\ &= \text{Date of last/latest dose} \\ &\quad - \text{Date of first placebo or bimekizumab dose} + 1 \end{aligned} \quad (38)$$

$$\begin{aligned} \text{Days on bimekizumab treatment} \\ &= \text{Date of last/latest dose} \\ &\quad - \text{Date of first bimekizumab dose} + 1 \end{aligned} \quad (39)$$

10.2 Adverse events

An AE is any untoward medical occurrence in a patient or clinical investigation subject administered a pharmaceutical product that does not necessarily have a causal relationship with this treatment. An AE can therefore be any unfavorable and unintended sign (including an abnormal laboratory finding), symptom, or disease temporally associated with the use of a medicinal (investigational) product, whether or not related to the medicinal (investigational) product.

AEs (including serious AEs) are characterized as either non-treatment or treatment emergent according to the following criteria:

- Non-treatment emergent are the events with onset date and time prior to the very first administration of study medication (bimekizumab or placebo) or after a 140-day period after the final drug administration.
- Treatment-emergent AEs (TEAE) are those with onset date at or after the very first administration of study medication. The events that emerge within 140 days after the final drug administration, will also be considered as treatment emergent (eg, in the case of premature discontinuation or during the Safety Follow-up [SFU] period).

All AEs occurring during the study (i.e., after signature of the informed consent document) will be recorded in the eCRF. For each AE the following information will be recorded in the eCRF: AE term (verbatim term), date of onset, whether or not the AE was classified as a SAE, as an AE of special interest, intensity, relationship to study medication, action taken with study medication, other action taken, outcome, date of outcome, and whether the AE led to study drug discontinuation or to study discontinuation.

ADRs are defined as a response to a drug which is noxious and unintended and which occurs at doses normally used in man for prophylaxis, diagnosis, or therapy of disease or for modification of physiological function. Any AE that is considered "Related" to study treatment will be classed as an ADR.

If an AE occurs on the same day as the treatment switch (Visit 7, Week 12) then the AE will be allocated to the Double-Blind treatment. An exception from this general rule is made for ADRs, and AE of hypersensitivity reactions and anaphylactic reactions. If those AEs occur on the same days as the treatment switch, the AEs will be allocated to the Dose-Blind treatment.

The incidence of TEAEs will be summarized by MedDRA SOC, high level term, and PT. Tables with incidences of classified TEAEs by maximum intensity, by relationship, and by subject number will be provided. The incidence of non TEAEs, non-serious TEAEs above the reporting threshold of 5% of subjects and relationship will be summarized. Furthermore the incidence of all TEAEs, serious TEAEs, non-serious TEAEs, and TEAEs leading to study discontinuation and/or permanent withdrawal of study medication, adverse drug reactions, fungal infectious disorder TEAEs, opportunistic infection (including tuberculosis) TEAEs, malignant or unspecified tumor TEAEs, malignant tumor TEAEs, major cardiovascular event TEAEs, haematopoietic cytopenias TEAEs, neuropsychiatric events TEAEs, inflammatory bowel disease TEAEs, hypersensitivity and anaphylactic Reaction TEAEs, hepatic events TEAEs, and TEAEs by timing of onset relative to AbAb Status will be summarized. In addition, an overall summary table will be provided.

The tables will be split into the Double-Blind Period and the complete treatment period (exception non TEAE table and TEAEs by timing of onset relative to AbAb Status).

Presentations for the Double-Blind Period will summarize AEs that start prior to or at Visit 7 (see details given above) by treatment group as randomized for the Double-Blind Period.

Presentations for the complete treatment period will only summarize AEs that occur under treatment with bimekizumab, irrespective of the treatment period. For summaries of the bimekizumab 160mg, 160mg with loading dose and bimekizumab 320mg treatment groups, patients randomized to Placebo or bimekizumab 16mg at Baseline will only be included with AEs that start in the Dose-Blind Period. The all bimekizumab treatment group will also present AEs occurring under bimekizumab 16mg treatment in the Double-Blind Period. AEs for each subject will be summarized based on the treatment actually received at the onset of each particular AE.

Exposure adjusted incidence rate (EAIR) and exposure adjusted event rate (EAER) will only be calculated for the complete treatment period for following tables in the final analysis: all TEAEs, serious TEAEs, TEAEs leading to study discontinuation and/or permanent withdrawal, adverse drug reactions, fungal infectious disorder TEAEs, opportunistic infection (including tuberculosis) TEAEs, malignant or unspecified tumor TEAEs, malignant tumor TEAEs, major cardiovascular event TEAEs, haematopoietic cytopenias TEAEs, neuropsychiatric events

TEAEs, inflammatory bowel disease TEAEs, hypersensitivity and anaphylactic Reaction TEAEs, hepatic events TEAEs, and TEAEs by timing of onset relative to AbAb Status.

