10.2.2 Exposure adjusted incidence rate (EAIR) and exposure adjusted event rate (EAER)

The EAIR is defined as the number of subjects (n_{AE}) with a specific AE adjusted for the exposure and will be scaled to 100 patient-years:

$$EAIR = 100 * \frac{n_{AE}}{\sum_{i=1}^{n_{AE}} T_{Exp,i} + \sum_{j=1}^{n_{noAE}} T_{Risk,j}} \quad (43)$$

where $T_{Exp,i}$ is a subject's exposure time in years up to the first occurrence of the AE of interest (equation [40] in years) at the level of coding evaluated, n_{noAE} the number of subjects without the specific AE and $T_{Risk,j}$ the total time at risk scaled to 100 patient-years (Section 10.1).

If a subject has multiple events at the level of coding evaluated, the time of exposure is calculated to the first occurrence of the AE of interest. If a subject has no events, the total time at risk (Section 10.1) in years is used. As indicated above, exposure-adjusted incidence rates will only be calculated for the overall treatment period. These presentations do not include AEs that occur under Placebo treatment. Therefore, a subject's exposure time will only start at the first dose of bimekizumab in the Dose-Blind Period for subjects randomized to Placebo at Baseline. Also, for subject's randomized to bimekizumab 16mg at Baseline, exposure time will only be

considered from the start of Dose-Blind Period, when presenting AEs for the bimekizumab 160mg and bimekizumab 160mg with loading dose, or bimekizumab 320mg groups. All exposure time on any bimekizumab dose is considered for the all bimekizumab column.

Exact Poisson 95% CIs for incidence rates are calculated using the relationship between the Poisson and the Chi-square distribution (Ulm, 1990; Fay and Feuer, 1997):

$$LCL = \frac{\chi_{2n, \frac{\alpha}{2}}^2}{2} \quad (44)$$

$$UCL = \frac{\chi_{2(n+1), 1-\alpha/2}^2}{2} \quad (45)$$

$$CI_{Lower} = 100 * \frac{LCL}{\sum_{i=1}^{n_{AE}} T_{Exp,i} + \sum_{j=1}^{n_{noAE}} T_{Risk,j}} \quad (46)$$

$$CI_{Upper} = 100 * \frac{UCL}{\sum_{i=1}^{n_{AE}} T_{Exp,i} + \sum_{j=1}^{n_{noAE}} T_{Risk,j}} \quad (47)$$

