where n_{AE} is the number of subjects with a specific AE for the incidence rate of interest and is the basis for the number of the degrees of freedom for the chi-square quantile for the upper tail probability χ^2 , $T_{Exp,i}$ is a subject's exposure time in years up to the first occurrence of the AE of interest (equation [40] in years) at the level of coding evaluated, n_{noAE} the number of subjects without the specific AE and $T_{Risk,j}$ the total time at risk scaled to 100 patient-years (Section 10.1).

The EAER will be the number of AEs including repeat occurrences in individual subjects divided by the total time at risk scaled to 100 patient-years and calculated using:

$$EAER = 100 * \frac{N_{AE}}{\sum_{j=1}^{n_{All}} T_{Risk,j}} \quad (48)$$

where N_{AE} is the total number of AEs, $T_{Risk,j}$ is a subject's total time at risk in years and n_{All} the number of subjects.

No CI will be computed for EAER.

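### Exposure-adjusted AE rates by timing relative to AbAb status use person-time that is never split at AbAb onset, so comparisons in that table can mislead in either direction

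*SAP*

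**What the plan says.** SAP 10.2 states: "Exposure adjusted incidence rate (EAIR) and exposure adjusted event rate (EAER) will only be calculated for the complete treatment period for following tables". The list that follows ends with "hepatic events TEAEs, and TEAEs by timing of onset relative to AbAb Status". The same section splits AE tables into the Double-Blind Period and the complete treatment period and exempts this table from that split: "exception non TEAE table and TEAEs by timing of onset relative to AbAb Status". The exemption says nothing about person-time.

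SAP 10.2.2 gives one general definition of each rate:

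- **EAER (equation 48):** all events, repeats included, "divided by the total time at risk scaled to 100 patient-years". The sum runs over n_All, described only as the number of subjects.
- **EAIR (equation 43):** a subject with the event contributes "exposure time in years up to the first occurrence of the AE of interest". For the others: "If a subject has no events, the total time at risk (Section 10.1) in years is used".
- **Confidence limits for the EAIR (equations 46 and 47):** the same denominator as equation 43.

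SAP 10.1 starts time at risk at the first injection, or at the first Dose-Blind injection where earlier placebo or 16mg time is not counted. It ends at the Week 48 visit for extension entrants and at death for subjects who die. For all others it ends at the earlier of final contact and 140 days after the last injection.

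SAP 9.2 defines the visit of first AbAb positivity. It sets that visit to Baseline for subjects who were positive at Baseline and later show a four-fold titre rise. No denominator uses this visit.

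**The concern.** A rate can be interpreted only if every unit of time in the denominator could have produced an event in the numerator. An event after AbAb onset cannot occur before onset, yet the pre-onset weeks of an AbAb-positive subject stay in the denominator. The same mismatch affects events before onset.

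The SAP applies the matching principle elsewhere. SAP 10.2.2 restarts the clock at the first bimekizumab dose for placebo starters, because AEs under placebo are excluded. It does the same for 16mg starters in the 160mg and 320mg columns. Only the AbAb-timing table restricts the numerator without restricting the time, which looks like an omission rather than a choice.

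Safety and immunogenicity are both secondary objectives (SAP 2.1.2), and this table links them. A reader would compare the after-onset rate with the rate in never-positive subjects, or with the before-onset rate. Both comparisons are distorted, and not in the same way.

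**Working it through.** The documents give no rate, seroconversion share or onset time for this table, so there is no planned figure to reproduce. The check applies the stated formulas to an assumed cohort.

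**Inputs from the SAP.** Equations 43 and 46 to 48 (10.2.2), time at risk (10.1), visit of first AbAb positivity (9.2).

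**Assumptions, not from the documents.** T = 48 weeks at risk; 100 events per 100 patient-years (PY) without antibody; true rate ratio 2 after onset; onset t at Week 4 to 36; AbAb-positive share p of 20% to 50%.

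**EAER, each stratum using its own subjects' whole time.** An AbAb-positive subject is expected to have 100 × t events before onset and 200 × (T - t) after it, in units of 100 PY. Equation 48 divides both by T:

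- before = 100 × t/T, against a true 100
- after = 200 × (T - t)/T, against a true 200
- never-positive = 100, which is correct because no split is needed

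**EAER, n_All read as all subjects.** The after-onset rate is multiplied again by p.

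| Onset | Factor before, t/48 | Factor after, (48 - t)/48 | Before (true 100) | After (true 200) | After/before (true 2) | After/never-positive (true 2) | After, all subjects, p = 30% |
|---|---|---|---|---|---|---|---|
| Week 4 | 0.08 | 0.92 | 8.3 | 183.3 | 22 | 1.83 | 55 |
| Week 12 | 0.25 | 0.75 | 25 | 150 | 6 | 1.50 | 45 |
| Week 24 | 0.50 | 0.50 | 50 | 100 | 2 | 1.00 | 30 |
| Week 36 | 0.75 | 0.25 | 75 | 50 | 0.67 | 0.50 | 15 |

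With time split at onset, the after-onset EAER is 200 in every row. With all subjects in the denominator, the Week 12 figure of 45 becomes 30 for p = 20% and 75 for p = 50%.

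**No true effect, onset at Week 12.** The rates shown are 25 before, 75 after and 100 in never-positive subjects. The after/before ratio is 75/25 = 3 and the after/never-positive ratio is 0.75. The same data look harmful in one comparison and protective in the other.

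**Other values of T.** Placebo starters who enter the extension have about 36 weeks on bimekizumab (Week 12 to Week 48). Onset 12 weeks into that time gives an after-onset factor of (36 - 12)/36 = 0.67. A subject who completes dosing to Week 44 and does not enter the extension can have 308 + 140 = 448 days, or 64 weeks. Onset at Week 12 then gives (64 - 12)/64 = 0.81.

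**EAIR, prose definition.** Because subjects with the event stop at first occurrence, the factors above are not exact. In simulation (200,000 subjects, p = 30%, true after-onset rate about 40 per 100 PY), the EAIR was about 36, 29, 20 and 9 for onset at Weeks 4, 12, 24 and 36 with AbAb-positive subjects only. With all subjects it was about 10, 8, 6 and 3. It was understated in every run, over base rates of 5 to 200 per 100 PY.

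**A cross-reference that matters here.** For time to first occurrence, equation 43 points to equation 40, which is AE duration. Taken literally, this can push the EAIR the other way: 306 against a true 203 for AbAb-positive subjects only, base rate 100 per 100 PY, onset at Week 12 and an assumed AE duration of 10 days.

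**The case against.** The strongest objection is that the SAP never sets out the strata of this table. Only its name appears, and table layouts sit in separate TFL shells (SAP 4.3.1) that are not among the documents. The shells might define suitable denominators. This stands as a limit on certainty: the before/after layout is inferred. It does not remove the point. SAP Section 1 says the plan provides everything needed for the analysis, and a programmer who follows it is led to equations 43 and 48.

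A second objection is that the table is descriptive and tests no hypothesis. AbAb results are also listed by subject, the timing of first positivity is summarized (SAP 9.2), and hypersensitivity and anaphylactic reactions have their own table (SAP 10.2.3). This is fair and limits the consequence. None of those outputs gives a rate before or after AbAb onset, so none corrects this one.

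A third objection is that splitting person-time brings its own error, because seroconversion is dated only to a sampling visit. Under Protocol Section 8, no scheduled visit between Weeks 24 and 36, or between Weeks 36 and 48, includes an AbAb sample. Up to 12 weeks after true seroconversion could therefore be counted as before onset. This stands and belongs in a footnote. It is a smaller problem than leaving all pre-onset time in the after-onset denominator.

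**Conclusion.** The point holds: the SAP requires these rates and gives them denominators that do not match the events counted. If events are split at AbAb onset, the after-onset EAER is understated by the factor (T - t)/T. In the 48-week illustration the shortfall runs from 8% (onset at Week 4) to 75% (Week 36). If all subjects enter the denominator it is 54% to 95%, for a positive share of 50% down to 20%. The after-onset EAIR under its prose definition is also too low. These sizes rest on the assumed follow-up, onset times and positive share; the direction of the after-onset EAER error does not.

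A reader might infer that the table always masks antibody-related harm, or makes seroconversion look protective. The documents do not support that. It applies to the comparison with never-positive subjects when each stratum uses its own subjects' time. With all subjects in every denominator, that comparison also depends on the positive share: a true ratio of 2 with onset at Week 12 shows as 0.64 at 30% positive and 1.50 at 50%. Within AbAb-positive subjects, onset before the midpoint of follow-up exaggerates the before/after contrast. Nor can one say that every rate comes out too low, given the literal reading of equation 43's pointer to equation 40.

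The primary analysis is unaffected. The correction should be made before the table is produced.

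**What to change.** Add a paragraph to SAP 10.2.2, for this table only, that defines three strata of person-time:

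- **(a) Never AbAb-positive:** all time at risk on bimekizumab.
- **(b) AbAb-positive, before onset:** first bimekizumab dose to the day before the first AbAb+ visit.
- **(c) AbAb-positive, after onset:** first AbAb+ visit to the end of time at risk. Subjects whose first occurrence is set to Baseline under SAP 9.2 contribute only to (c).

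Use each stratum's own subjects and time in equations 43 and 46 to 48, and say so in place of the unqualified n_All. Count time to first AE from the start of the stratum to AE onset, not AE duration (equation 40). For the 160mg and 320mg columns, keep the clock start already given in SAP 10.1. Add a footnote that onset is known only to the sampling visit, so some time after true seroconversion is counted as before onset.

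The cost is one paragraph, a footnote and a small programming change to one table. All dates needed are already defined, and no new data are required.
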